 Yes	 X No (If Yes, please contact PRO for a separate review)
------------------------------	-------------------------------------------------------------------------------------------------------------

9. Additional Reviews

a) Has the research project received a scholarly, scientific, or peer review prior to this submission (this may involve a review by a funder, faculty supervisor, or a departmental committee):

 Yes, specify: [name], [name]
 No (NB: IRB recommends a prior scholarly review for studies that are more than minimal risk)
 Pending, specify:

b) Will this research require review by any of the following (check all that apply):

None – UCR IRB is the only approval required

Other (e.g., UCR or non-UCR entities – such as UC [Reliance](#) Registry, [SMART IRB](#) or another IRB)

Specify entity and status of review:

UCR Institutional Biosafety Committee ([IBC](#)): Research using biohazardous materials including any human-derived materials such as blood, body secretions, and tissues, primary and established cell lines

UCR Stem Cell Oversight Committee ([SCRO](#)): Research using human pluripotent cells

UCR Institutional Animal Care and Use Committee ([IACUC](#)): Research using vertebrae animals

II – Study Summary

10. Abstract (suitable for a lay audience)

(Max ¼ page)

In this study we will evaluate the impact of a pre-operative instructional video for patients undergoing a minimally invasive gynecologic surgery. The video will educate patients to understand what to expect and how to take care of themselves after the procedure. The effectiveness of the video will be evaluated via a questionnaire to see if patient's who watched the video had better recovery outcomes, greater understanding, and less anxiety when compared to the group of patients who did not watch the pre-operative video.

11. What is the scholarly rationale for this study?

(Max ½ page)

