The study group of patients will come to the clinic on the day of their surgery and be asked to watch the informational video about what to expect after their procedure and instructions on how to recover. They will be encouraged to ask their provider any follow up questions. [The instructional video is approximately 10 minutes long.](#)

The control group of patients will receive the standard patient education in place before the procedure and will also be able to ask to follow up questions from their provider.

Both groups will be scheduled for their routine two-week postoperative visit. Some patients schedule a telehealth postoperative visit, if a telehealth visit is scheduled, then a text or email will be sent. If the patient comes in person, the option of filling out the questionnaire in paper form, receive text or email to complete the survey. [The survey will take approximately 10 minutes to complete.](#)

Our primary outcomes will be patient level of satisfaction with the education they received prior to surgery and its impact on post-operative care which will be measured by the standardized likert scale (1 to 5 scale where 1 = strongly disagree and 5= strongly agree). The survey will include the following objective and subjective measures: Tylenol tablets used (over two weeks), Ibuprofen tablets used (over two weeks), pain scale (1 to 5 scale where 1 = none and 5= very severe). Additional information will be collected from the patient's medical records (ie. office visit notes, telephone encounters, hospital laboratory results, pain medication refill requests). Patients should continue any medication regimen as instructed by their physician up to the day of surgery. Patients will be treated for complications as they would have been treated otherwise. Study duration period will be approximately six months.

b) If you are using a dataset, please list out the variables you will be accessing. If you are using the Psychology Subject Pool, please list out the pre-screening data you will be collecting on your participants.

(Max ½ page)

[Chart review data: Age, Ethnicity, BMI, Smoking status, Narcotic use before surgery, Pain levels before surgery, Preop hemoglobin, Indication for surgery, Surgical procedure, Diagnosis, Presence of other pain disorders such as Interstitial cystitis, fibromyalgia, Intraoperative complications,](#)

[and Intraoperative blood loss.](#)

REDCAP Database will be used for the following purposes:

- Data collection

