25. Withdrawal: Where applicable, please describe how participants will be informed of their right to withdraw from the study and outline the procedures that will be followed to allow them to exercise this right. Also, what will happen if data has already collected (e.g. previous data will be kept, all data will be destroyed, etc.)?

(Max ¼ page)

Participants or legal representatives will be informed of their right to withdraw from the study at any time, verbally and via the written informed consent form. If the patient wishes to withdraw from the study, the data collected will be discarded.

Participants may be withdrawn at any time during the study, until its completion, at which point the de-identified data will not be able to be withdrawn because the identifying data will have been destroyed and link between coded and records is deleted, projected end 2024. Also, published coded/de-identified data will not be able to be withdrawn.

Procedures for withdrawal will be as follows: access to the key code by approved personnel on the project roster, removal of that coded data from all files, shredding of written records, deletion of electronic records.

26. Privacy, Confidentiality & Data

a) **Privacy: Where and how will participants be providing information? Are the researchers collecting identifying information (e.g., names, addresses, phone numbers, DOBs, phone numbers, licenses, audio/video recordings, etc.)? If yes, please describe:**

(Max ¼ page)

Patient identifying data will be provided via the informed consent and will include name, date of birth, medical record number, address, phone number, email address, and an alternate contact if the patient or legal representative is unavailable. A study number, for example given by REDCAP will be given to each subject P01, with "P" representing patient with a numerical value thereafter will be transcribed on the consent form and the medical questionnaire. The coded medical questionnaire will be completed for pertinent medical history. The documents with identifying information (consent form, HIPAA), will be placed in a sealed envelope for collection, or saved electronically on a password-protected drive, and stored in the office of the clinical PI

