b) Describe the possible risks and consider the probability and magnitude of possible harms and discomforts. Describe the procedures that will be used to minimize potential risks to participants.

(Max ¼ page)

A remote unlikely risk is that the patient could feel more anxiety towards surgery despite the educational videos effort to calm patients concerns. The patient will be validated in her fears and reiterate that the video is meant to improve a patient's understanding regarding upcoming surgery. The patient will also be reassured that she can chose to be removed from the study at any point.

Ethical concerns may be associated with reviewing medical records of each participating patient but in order to prevent release of information improperly, each participating individual including physicians, nurses, receptionists, and the principal investigator will be certified under HIPPA and will properly exercise HIPPA regulations throughout the duration of this research.

- Only members of the study team will have access to the study data
- All study documents will be maintained in a secure location (i.e., a locked cabinet in the locked study coordinator's office [with limited access]) with only authorized research personnel affiliated with the study having access to it
- All electronic data will be stored on a password protected database with encryption, firewall, etc.

28. Possible Benefits

a) Describe possible direct benefits to participants. If there are no direct benefits, please state so. Please note that compensation is not a benefit.

(Max ¼ page)

Taking part in this study may or may not make benefit the subject's health. All reasonable efforts will be made to ensure the safety of each participant by following good medical practice guidelines. Any unanticipated risks will be addressed on a case-by-case basis.

b) Describe possible benefits to communities, society, or scientific knowledge in general.

(Max ¼ page)

The information from this study might help to develop better post operative experience after receiving concise information via video for future patients undergoing similar surgeries.

29. The US research regulations define '*Minimal Risk*' as the probability and magnitude of physical or psychological harm that is normally encountered in the daily lives, or in the routine medical, dental, or psychological examination of healthy persons. (45 CFR 46 & 21 CFR 50)

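### An anxiety-triggered reminder about leaving the study exists only for the video arm, and leavers' data are discarded, so patients who respond badly to the video may be selectively lost

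*Combined protocol and SAP*

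**What the plan says.** Section 27b names one harm of the intervention: "A remote unlikely risk is that the patient could feel more anxiety towards surgery despite the educational videos effort to calm patients concerns". The response has three parts. The first two are: "The patient will be validated in her fears and reiterate that the video is meant to improve a patient's understanding regarding upcoming surgery". The third is: "The patient will also be reassured that she can chose to be removed from the study at any point".

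For controls, section 20a says: "The control group of patients will receive the standard patient education in place before the procedure". They may also put questions to their provider. Nothing is said about what happens if a control patient becomes anxious.

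Section 25 covers both arms alike: "Participants or legal representatives will be informed of their right to withdraw from the study at any time, verbally and via the written informed consent". On data already held it says: "If the patient wishes to withdraw from the study, the data collected will be discarded". The procedure there removes the coded data from every file and destroys paper and electronic records.

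The outcomes at stake are satisfaction (section 20a: "Our primary outcomes will be patient level of satisfaction with the education they received prior to surgery") and the expectation in the section 10 abstract of "greater understanding, and less anxiety when compared to the group of patients who did not watch the pre-operative video". The video is shown on the day of surgery, and the survey is completed around the two-week visit.

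**The concern.** The reminder is prompted by a bad reaction to the intervention, which is the reverse of the benefit the trial hopes to show. An equally anxious control patient has the same right to leave, but the plan does not describe anyone reminding her of it at that moment. The route out of the study can therefore differ by arm, and differ according to response.

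Two other features add to this. Section 27b mentions leaving but not the alternative of finishing with the video and staying in follow-up. Under section 25 a leaver's data are then discarded, so both her outcome and the record of why she left could disappear. If this happened more than rarely, the comparison would tilt toward the video, and the trial would under-report the one harm it names.

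**Working it through.** **1. The plan's own figure.** Section 15 gives 100 patients in total for a difference of 20% or greater. It states no alpha, sidedness, power, control rate, SD or allocation ratio, so the figure can be neither reproduced nor refuted. It is used here only to assume 50 per arm.

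**2. The sections side by side.**

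| Point | Video arm | Control arm |
|---|---|---|
| Told of the right to withdraw, verbally and in writing (section 25) | Yes | Yes |
| Reminded of it when the education raises anxiety (sections 27b, 20a) | Yes | Not described |
| Offered the choice to stop the education but stay in follow-up | Not described | Not described |
| Data discarded on withdrawal (section 25) | Yes | Yes |

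Only the second row differs by arm. The third and fourth rows allow that difference to turn into lost data. Because the video precedes the survey by about two weeks, a patient who leaves after the video supplies no survey outcome. The plan defines no analysis population and no missing-data method that would offset this.

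**3. Shift in a satisfaction proportion.** Assumptions: 50 per arm, no true effect, 35/50 = 70% satisfied in each arm, every leaver dissatisfied, no control leaves. With k leavers the video rate is 35/(50 − k).

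| k | Video rate | Shift from 70% |
|---|---|---|
| 1 | 35/49 = 71.4% | +1.4 points |
| 3 | 35/47 = 74.5% | +4.5 points |
| 5 | 35/45 = 77.8% | +7.8 points |

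With 50% satisfied, one leaver gives 25/49 = 51.0% (+1.0) and five give 25/45 = 55.6% (+5.6). If leavers were no less satisfied than those who stay, the expected shift would be zero.

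**4. Shift in a 1-to-5 mean.** Let a fraction p leave, with scores d points below the mean s of those who stay. The full-arm mean is (1 − p)s + p(s − d) = s − pd, so losing them raises the observed mean by pd. With d = 1 (assumed), one leaver gives 0.02 × 1 = 0.02 points, three give 0.06 and five give 0.10.

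**5. Effect on the test.** This is a simulation of 20,000 null trials with 50 per arm, a normal outcome and a two-sided t-test at 0.05, all assumed. The k most anxious video patients are deleted. The correlation between anxiety and outcome is set at 0.5 or 1.

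| k | Bias toward video, SD (correlation 0.5 / 1) | Type I error (0.5 / 1) |
|---|---|---|
| 1 | 0.02 / 0.04 | about 5% / 6% |
| 3 | 0.06 / 0.12 | about 6% / 10% |
| 5 | 0.10 / 0.19 | about 8% / 17% |

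For scale, the difference detectable with 80% power is (1.960 + 0.842) × √(2/50) = 0.56 SD.

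**The case against.** The other side has a good case, and much of it stands.

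- A reader might infer that the video's worst responders are in fact removed. The documents do not say so. Section 27b restates a voluntary right, for an event it regards as remote, and no withdrawal rate appears anywhere.
- A reader might infer that controls are not told they may leave. Section 25 tells every participant. What is particular to the video arm is one further reminder. The consent form is not in the public copy, so what else each arm is told cannot be checked.
- A reader might infer that removal is the only response to anxiety. It comes last, after staff acknowledge the patient's fears and restate the purpose of the video, and section 20a encourages video patients to ask questions.
- The video is a single viewing of about 10 minutes, so an already distressed patient may have little left to stop. This is fair. The useful part of the added option is therefore staying in follow-up.
- Bias in the primary outcome needs a link between anxiety on the day of surgery and satisfaction two weeks later, and that link is unknown. The survey measures listed in section 20a include no anxiety item, although section 10 expects the questionnaire to address anxiety.
- Reminding a distressed participant that she may leave is an ordinary ethical safeguard. Removing it to avoid a bias that may be small would be a poor trade.

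What remains is narrower: a trigger specific to one arm, no stated option to stay, and a rule that discards the leaver's data.

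**Conclusion.** The point holds as a risk of differential loss. It does not show that bias will occur. The direction is fairly clear: losses through this route would probably favour the video on anxiety and possibly on satisfaction. The size is unknown. If one video patient left, the effect would be negligible (+1.4 percentage points, or 0.02 to 0.04 SD). If five left, it would be noticeable (+7.8 points, or 0.10 to 0.19 SD, with type I error of about 8% to 17%), though still well below the 0.56 SD detectable difference. These figures assume 50 per arm and no matching loss among controls. The percentage figures also assume 70% satisfied and every leaver dissatisfied; the SD figures assume a correlation of 0.5 to 1 between anxiety and outcome. Because section 25 discards leavers' data, the trial might be unable to show afterwards that the loss was small. A cheap improvement is warranted; the design itself need not change.

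**What to change.** Keep the right to withdraw and the reminder in section 27b. Then:

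1. Add to section 27b, for any patient in either arm who reports anxiety about the education, that she may decline or stop the education material and remain in the study. The two-week survey and chart review continue unless she asks to leave.
2. Record in REDCap, by arm, each report of increased anxiety, each video not completed, and each withdrawal with its reason.
3. Amend section 25 so that data collected before withdrawal are kept where consent permits. This preserves baseline data and the record of the event. It does not recover a survey that was never completed, which is why the first change matters most.

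The cost is a few sentences in two sections, a few REDCap fields, and consent wording that agrees with the amended section 25. The downside is that a few patients with incomplete exposure stay in the video arm, which slightly dilutes its apparent effect.

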IRB applications must be submitted via email ([contact]) with the required signatures in place. The application should be submitted as a single attachment in PDF or Word format. All the appendices are to be inserted in the single attachment in the order that they are listed in question Q30 with descriptive headers to facilitate cross-referencing and review of the application.

If this application is more than minimal risk, please note the submission deadlines for IRB meetings on our website. Ultimately, the IRB may choose to escalate an application for full board review if it deems the level of risk to be more than minimal. While this is a subjective assessment, it is not a haphazard one. For additional guidance and assistance, please visit the ORI IRB [FAQ's](#) and [Resources](#) pages.

For student/trainee or UCR-faculty sponsored IRB applications, all 3 signatures are required (student/trainee + UCR faculty + chair). For faculty research, only two are required (faculty + chair).
